Sample size calculations were performed using GLIMMMPSE Version 3.⁴³ Though a Bayesian model averaging approach will be used, sample size calculations using a non-Bayesian approach are applicable here because they correspond to the model that is believed to be most likely true *a priori*, and also because we plan to use uninformative priors on the parameters in the model, which makes our analyses comparable to the non-Bayesian approach that is used for sample size calculations. As we do not have pilot data to inform our sample size calculations for the NAS/non-NAS group, our sample size calculations are based on the group means by gender that were observed in the pilot study on “total puffs” and a standard deviation of 5.5.³¹ Given NAS smokers’ preexisting misperceptions about natural/organic cigarettes, we anticipate that group means will be more extreme in the NAS/non-NAS group.⁴⁴ Thus, the minimum sample size required for Aim 3 analyses should be sufficient to address the Aim 2 analyses. Assuming an intraclass correlation between repeated measurements of 0.5, 40 total subjects are needed to detect a significant interaction between gender and condition (natural/organic vs conventional/own brand) at 90% power and a significance level of 5%, while 99% power requires 68 subjects. Since these assumptions use information based on only 22 subjects in the pilot study, sample size calculations were also performed with an effect size 50% smaller and a

covariance matrix 50% larger than assumed: under these conditions, 90% power is achieved with 228 total subjects. Fewer subjects are needed to detect differences hypothesized in Aim 1 at each given power; for example, under the smallest effect size observed in the topography pilot data (which assumes a mean difference of 120ml with standard deviation 165ml), 120 subjects are needed to achieve 90% power under an effect size that is 50% smaller and covariance matrix that is 50% larger than assumed. Thus, we will enroll 125 participants per cigarette type (250 total, though we have budgeted for up to 300 participants to account for loss to follow up) to ensure at least 228 participants complete the full study. Our proposed sample size is adequate to detect a similar topography effect size to our pilot study, examine moderation by NAS preference and gender, and allow for adjustments to the significance level due to multiple comparisons.

Statistical analyses

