H(1.1), H(2.1), H(3.1): Expectancies (Have fewer chemicals)

We will create a binary variable from a 5-point Likert scale (Definitely true, Somewhat true, Neither true nor false, Probably false, Definitely false) for this measurement to indicate if the participant believes the cigarettes smoked during the visit have fewer chemicals (if answered Definitely true or Somewhat true) or not (if answered Neither true nor false, Probably false, or Definitely false). We will use an approach that models the probability of belief that cigarettes smoked during the visit have fewer chemicals, and we will use the logit link function so that the form of the best model will resemble a mixed effects logistic regression model; other link functions (e.g. probit) will be considered if model fit is a concern.

H(1.2), H(2.2), H(3.2): Subjective effects (chemical aftertaste)

Chemical aftertaste will be used as the outcome, which will have items rated on a 100 mm visual analog scale with item-specific anchors (e.g., strength: 0 = "strong chemical aftertaste," 100 = "no chemical aftertaste"). We do not anticipate many measurements on the boundaries (0 or 100), which makes Normality an appropriate assumption for the residuals. However, if there are many measurements on the boundaries (i.e. if Normality does not seem like an appropriate assumption for the residuals), then a binary outcome that indicates if the measurement is greater than 50 will be used instead, and we will use the logit link function so that the form of the best model will resemble a mixed effects logistic regression model (like above for the expectancies outcome); other link functions (e.g. probit) will be considered if model fit is a concern.

H(1.3), H(2.3), H(3.3): Topography (total puff volume)

Normality is expected to be an appropriate assumption for total puff volume (a quantitative variable) based on pilot data.³² However, if Normality does not seem like an appropriate assumption for the residuals in this sample, then a transformed outcome (e.g. log-transformation) will be considered (particularly if the outcome is skewed). If normality is still violated, we will consider a binary outcome using a median cutoff and use the logit link function so that the form of the best model will resemble a mixed effects logistic regression model (like above for the expectancies outcome); other link functions (e.g. probit) will be considered if model fit is a concern.

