H(1.4), H(2.4), H(3.4): Biomarkers of exposure (Salivary aldehydes)

Concentrations of formaldehyde and acetaldehyde will be used as the outcome (difference between pre- and post-visit), where Normality is expected to be an appropriate assumption for the error term. However, just as with the other outcomes, if Normality does not

seem like an appropriate assumption, a transformed outcome (e.g. log-transformation) will first be explored, and if normality still does not hold, then we will consider a binary outcome using a median cutoff and use the logit link function so that the form of the best model will resemble a mixed effects logistic regression model (like above for the expectancies outcome); other link functions (e.g. probit) will be considered if model fit is a concern.

Hypothesis testing

H(1.1 - 1.4) are primary, and under the null hypotheses in H(1.1 - 1.4), the natural and organic condition means are equal to the conventional condition means. To test the hypotheses in Aim 1, we will first determine if the effects of the condition depend on gender and NAS-smoking status (as hypothesized in H(2.1) - H(3.4)). If the effect of the condition does not depend on gender or NAS-smoking status, then we will estimate the following effects in our model:

1. effect of the conventional condition
2. effect of the natural condition
3. effect of the organic condition

The null hypotheses in H(1.1 - 1.4) state that the conventional condition is equivalent to the natural and organic conditions. We can therefore test H(1.1 - 1.4) by estimating 95% credible intervals for the difference between the effects of the organic and natural conditions and the conventional condition. This will yield two credible intervals (one for the difference between natural and conventional effects, and another for the difference between organic and conventional effects) for each outcome (four outcomes) therefore making 8 total credible intervals of interest in Aim 1. If the effects of the condition depend on NAS-smoking status but do not depend on gender, then we will estimate the following effects in our model:

1. effect of the own brand condition for Non-NAS smokers
2. effect of the conventional condition for Non-NAS smokers
3. effect of the natural condition for Non-NAS smokers
4. effect of the organic condition for Non-NAS smokers
5. effect of the own brand condition for NAS smokers
6. effect of the conventional condition for NAS smokers

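### The fallback to a cut at 50 for chemical aftertaste, and the possible median splits for puff volume and aldehydes, replace the mean contrast on an undefined, data-dependent trigger

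*Combined protocol and SAP*

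**What the plan says.** The rules stand in the combined protocol and SAP, Statistical analyses, in the paragraphs on each group of hypotheses.

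- **Chemical aftertaste (H1.2, H2.2, H3.2).** The plan does not expect many ratings at the ends of the 100 mm scale. If there are many, or residual Normality looks doubtful, "then a binary outcome that indicates if the measurement is greater than 50 will be used instead", modelled with a logit link. No transformation or bounded-scale model comes first, and no threshold is given.
- **Total puff volume (H1.3, H2.3, H3.3).** A transformation such as the log is considered first. If Normality still fails, "we will consider a binary outcome using a median cutoff".
- **Salivary aldehydes (H1.4, H2.4, H3.4).** The order is the same: transformation, and if that fails, "then we will consider a binary outcome using a median cutoff". The outcome is a pre/post difference.

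Under Aims & Hypotheses, H1.2 is about participants' average ratings, H1.3 about total puff volume and H1.4 about change in concentration. Under Hypothesis testing, the Aim 1 null is equality of condition means. Sample size calculations gives no power for a dichotomised version of any of these outcomes.

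**The concern.** Three of the four primary outcomes can end as a yes/no variable after someone has looked at the residuals. Two things are then at stake.

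The first is the question answered. A logit model of exceeding 50, or of exceeding the sample median, estimates odds of crossing a line. A participant who moves from 60 to 90 on the aftertaste scale, or from 10 to 40, contributes nothing to it, although both moves count fully in H1.2. This holds whatever the power figures are.

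The second is information. Cutting a continuous measure at its median discards much of it, and the sample size section does not allow for that. Because the trigger has no number, two analysts with the same residual plot could reasonably choose different primary analyses.

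**Working it through.** **Inputs (Sample size calculations).**

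- Smallest pilot topography effect: "which assumes a mean difference of 120ml with standard deviation 165ml".
- Pessimistic scenario: "an effect size that is 50% smaller and covariance matrix that is 50% larger than assumed". This gives a difference of 60 ml and SD 165 × √1.5 = 202.1 ml.
- Correlation: "Assuming an intraclass correlation between repeated measurements of 0.5". The plan states this for the gender-by-condition calculation; carrying it to Aim 1 is an assumption.
- Stated requirement: 120 subjects for 90% power. Level 5%, sidedness not stated.
- Planned sample: 250 enrolled, "to ensure at least 228 participants complete the full study".

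**Step 1. Reproduce the plan's 120.** For a paired contrast, SD of the difference = 202.1 × √(2 × (1 − 0.5)) = 202.1 ml. Two-sided 5%: n = ((1.960 + 1.282) × 202.1 / 60)² = 119.2, so 120. A one-sided test gives 98, correlation 0.3 gives 167 and 0.7 gives 72, so the two-sided reading with 0.5 is the one that fits.

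**Step 2. Power on the continuous scale.** Standardised effect 60 / 202.1 = 0.297. Power = Φ(0.297√n − 1.960). At n = 228 this is Φ(4.48 − 1.96) = 99.4%.

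**Step 3. Power after a median split.** With Normal data, 44.1% and 55.9% of values lie above the common median. At correlation 0.5 the discordant proportions are 11.4% and 23.2%: sum ψ = 0.345, difference δ = 0.118. McNemar-type power = Φ((δ√n − 1.960√ψ) / √(ψ − δ²)). At n = 228 this is Φ((1.782 − 1.152) / 0.576) = 86.3%; simulation gives 87.3%.

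| n | Where it arises | Continuous | Median split | Loss (points) |
|---|---|---|---|---|
| 120 | plan's stated Aim 1 requirement | 90% | 60–61% | 29–30 |
| 228 | planned completers, pooled | 99.4% | 86–87% | 12–13 |
| 250 | planned enrolment, pooled | 99.7% | 89–90% | about 10 |
| 114 | half of 228: Aim 1 by brand group or by gender | 88–89% | 57–58% | about 30 |
| 57 | a quarter of 228: Aim 1 by both | 60–61% | 33% | about 28 |

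The last two rows assume equal groups and the same 60 ml effect in each. They matter because Hypothesis testing splits Aim 1 by group when the condition effect depends on brand preference or gender, and calls dependence on both the hypothesised case.

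**Step 4. A general check.** The efficiency of the median split relative to the mean is (2/π)(1 − ρ) / (1 − (2/π)·asin ρ) = 0.477 at ρ = 0.5. A contrast with 90% power falls to Φ(3.242 × √0.477 − 1.960) = 61%. About 257 people would be needed to restore 90% in the pessimistic Aim 1 scenario. The gender interaction, which the plan sizes at 90% with 228, would lose about 29 points if the same correlation and Normal model held.

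**Step 5. Other conditions.**

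- *Unreduced pilot effect (120/165):* the split keeps at least 99.9% power at n = 120 and above, so the pooled loss is near zero.
- *Heavy tails (t residuals with 3 df, assumed; Normal subject effects):* 98.9% against 96.4% at n = 228, and 89.8% against 78.4% at n = 120. If subject effects are also t with 3 df, the split does as well as the mean at 228 (99.4% against 98.6%).
- *Aftertaste:* no SD, effect or boundary rate is given, so this part is all assumption. A latent Normal scale was clipped to 0–100 with the same standardised effect and correlation. With latent mean 30 or 50 and SD 30 to 100 (10–62% of values on a boundary), the cut at 50 loses 9 to 16 points at n = 228. Other settings with 17–35% on a boundary give 12 to 25. The loss grows as 50 moves away from the centre of the data, so 25 is not an upper bound.
- *Is the switch needed?* In a clipped null case with 43% of values on a boundary and n = 228, the paired test of means kept its type I error at 5.0%.

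**The case against.** The strongest reply has four parts.

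1. **The loss at the planned size is modest.** The plan does not stop at 120. At 228 to 250 the pooled split still has about 86–90% power, close to the plan's 90% target, and the pilot effect leaves no visible loss. A reader might infer that the fallback costs about 29 points on the primary outcomes in general. The documents do not support that. The figure belongs to contrasts with about 90% power: a sample of 120, the by-group branches, or the secondary gender interaction under added assumptions.
2. **Normal data are not the data that trigger the rule.** This stands too. For puff volume and aldehydes the split is reached only when Normality fails, and with the heavy tails tried the loss at 228 was about 2 points or none. Skew and other shapes may behave differently.
3. **Two of the three rules are soft.** A reader might infer that the plan replaces all three outcomes as soon as residuals look non-Normal. It does so only for aftertaste. Transformation is weaker protection for aldehydes, though: the outcome is a difference, and a log cannot be taken of a zero or negative change.
4. **The calculations are paired frequentist tests**, while the plan uses Bayesian mixed models with covariates. The plan itself says these are comparable under uninformative priors, but the figures remain approximate.

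Ordinal or censored models also move away from the mean in H1.2. That is right, and it is why they belong in sensitivity analyses. None of this answers the change of question or the missing threshold.

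**Conclusion.** The point holds in a limited form. For chemical aftertaste the plan makes a cut at 50 the primary analysis on an unquantified trigger, so that the quantity tested is no longer the one in H1.2 or in the Aim 1 null. For puff volume and aldehydes the same could happen, but only as a considered last step. This conclusion rests on the text alone.

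The size depends on the case. It is about 12–13 points for pooled Aim 1 puff volume at 228 (pessimistic inputs, correlation 0.5, Normal data) and about 30 points where a contrast has about 90% power, such as groups of 114 with the same effect. It is near zero to 2 points under the full pilot effect or the heavy tails assumed. The aftertaste figure, roughly 9 to 25 points at 228, is indicative only. The calculations do not show an inflated error rate from the switch; the two-stage procedure was not examined. The plan should be changed, but the point does not undermine the sample size.

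**What to change.** - Keep the mean contrast from the linear mixed model, on the full 0–100, ml or concentration scale, as the primary analysis whatever the residuals look like.
- Pre-specify one full-scale sensitivity model per outcome, run regardless of the residuals. Examples are an ordinal or two-limit censored mixed model for aftertaste, and t-distributed residuals or a suitable transformation for puff volume and aldehydes. For the aldehyde difference, choose a transformation that can handle zero and negative changes.
- Report the proportion above 50, or above the median, only descriptively or as a further sensitivity analysis.

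Running the sensitivity model unconditionally removes the need to define how many boundary values are many. The cost is SAP wording, slightly more modelling, and a line explaining that ordinal or censored coefficients are not differences in observed means.

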Aim 1: Examine the association between exposure to “natural” or “organic” cigarette descriptors and: 1) health risk expectancies (e.g., chemical content); 2) subjective effects of smoking (e.g., chemical taste); 3) smoking topography (e.g., total puff volume); and 4) biomarkers of exposure (e.g., salivary aldehydes).

H_{1.1}: More participants will rate cigarettes in the “natural” and “organic” conditions as having fewer chemicals relative to cigarettes in the “conventional” condition.

H_{1.2}: Participants’ average ratings of the “chemical aftertaste” of the cigarettes in the “natural” and “organic” conditions will be higher (e.g., closer towards the “less chemical aftertaste” side of the scale) relative to their average ratings of the cigarette in the “conventional” condition.

H_{1.3}: Total puff volume will be higher in the “natural” and “organic” conditions than the “conventional” condition.

H_{1.4}: Change in salivary aldehyde concentrations pre/post administration of the study cigarette(s) will be higher in the “natural” and “organic” conditions than the “conventional” condition.

Aim 2: Examine whether the relationships in Aim 1 differ by preference for a “natural/organic” cigarette brand (NAS smokers vs. non-NAS smokers).

H_{2.1}: Compared to non-NAS smokers, more NAS smokers will rate the “natural” and “organic” conditions as having fewer chemicals relative to their ratings in the “conventional” condition, but not relative to their own brand condition.

H_{2.2}: Compared to non-NAS smokers, NAS smokers’ average ratings of the “chemical aftertaste” of the cigarettes in the “natural” and “organic” conditions will be higher (e.g., closer towards the “less chemical aftertaste” side of the scale) relative to their average ratings of the cigarette in the “conventional” condition, but not relative to their own brand condition

H_{2.3}: NAS smokers’ total puff volume will be lower in the “conventional” condition than the “natural,” “organic,” and own brand conditions.

H_{2.4}: NAS smokers’ change in salivary aldehyde concentrations pre/post study cigarette(s) administration will be lower in the “conventional” condition than the “natural,” “organic,” and own brand conditions.

Aim 3: Examine if relationships in Aim 1 differ by gender.

H_{3.1}: A greater proportion of women than men will rate the cigarettes in the “natural” and “organic” conditions as having fewer chemicals relative to cigarettes in the “conventional” condition.

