Total puff volume: We will collect participants' puffing behavior using a topography instrument developed and manufactured at the American University of Beirut and calibrated across labs to determine participants' total inhalation volume. To use the topography device, the cigarette is placed in a sterilized mouthpiece, and the internal pressure transducer measures pressure changes that occur during inhalation. The pressure changes are amplified, digitized and sampled at 1000 Hz, then software converts the signal to airflow (ml/s) in real time (s), and from this provides number of puffs, puff volume, puff duration, maximum flow, and interpuff interval (time between puffs). The primary topography outcome is total puff volume due to its well-characterized responsiveness to changes in cigarette type.³⁹⁻⁴¹

Biomarkers and saliva sample collection procedures

The primary purpose of the biomarker analysis is to assess whether exposure to aldehydes and nicotine in cigarette smoke varies by descriptor condition. These markers could reflect smoking behavior changes (i.e., mouth holding and inhalation) which could not be captured by topography measurement (i.e., puffing). Saliva samples will be collected from the participants before and after each ad lib tobacco product use bout in Sessions 2-5. The research

staff will ask subjects to wash their mouth with clean water when collecting the ‘before session’ saliva sample. The “after session” samples will be collected just after the participant finishes their last puff. Saliva samples (approx. 3 mL) will be collected using a Salimetrics saliva collection kit (Salimetrics, Carlsbad, CA). Saliva samples will be shipped to DRI Reno campus and be stored at -40°C prior to analysis. Salivary aldehydes (formaldehyde and acetaldehyde) and nicotine are exposure biomarkers. We will measure the concentration of these biomarkers in the mouth, before they are metabolized by the body, and make within-person comparisons in concentrations by study descriptor conditions. In addition, nicotine metabolites (cotinine and trans-3'-hydroxycotinine) will be measured to confirm smoking abstinence.

Missing data

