Baseline covariates that may be significant predictors of the outcome will be considered in the model because including predictors that reduce noise may increase the efficiency of the analyses in H(1.1) – H(3.4). We will use Bayesian model averaging to control for other covariates and estimate the parameters in each considered model.⁴⁹ Bayesian model averaging incorporates model uncertainty into inference and has several other advantages over the approach that relies on choosing a single best model among many candidate models.⁵⁰ In general, Bayesian model averaging uses all possible models that can be considered given a set of covariates (there are 2^k possible models when there are k covariates) and estimates parameters by using a weighted average of the estimates obtained from each model, where better fitting models are given larger weights (see Raftery et al. (1997)⁴⁹ and Hinne et al. (2020)⁵⁰ for more details). The following baseline measures in particular will be considered (which are *a priori* expected to be related to the outcomes that are used to test hypotheses H(1.1) – H(3.4)): score on the organic products scale, age, education, heaviness of smoking, perceived health, and own brand total puff volume (for all outcomes except the topography outcome, which uses total puff volume as the response); however, other covariates collected at baseline (e.g. race, ethnicity) will also be considered in the model. Using Bayes factors to first choose the best representation for the effects of the condition in the model and using Bayesian model averaging to estimate the parameters in the model will be repeated separately for each outcome, so that we have one model for each of the four outcomes: expectancies, subjective ratings, topography, and biomarkers of exposure.

A continuous response is a reasonable assumption for all outcomes except those in H(1.1), H(2.1), H(3.1), and H(4.1); in these hypotheses, the outcome will be modeled as a binary response (0/1) and an alternative model formulation (e.g. logistic mixed model) consisting of the same model parameters (e.g. same linear predictor as the other outcomes but using a logit link function) will instead be used to model the probability that the outcome is equal to 1. Other outcomes may also be modeled as a binary response depending on their distribution (more details are provided below).

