95% credible intervals will be estimated for the difference in effects between 9) 4. - 2. and 8. - 6., 10) 3. - 2. and 7. - 6., 11) 4. - 1. - (2. - 1.) and 8. - 5. - (6. - 5.), and 12) 3. - 1. - (2. - 1.) and 7. - 5. - (6. - 5.). If the credible interval in 9) / 10) does not contain 0, then there is evidence that men smokers mean outcome under the organic / natural condition relative to the convention condition differs from the women smokers mean outcome under the organic / natural condition relative to the convention condition, which would provide evidence against the null hypothesis in H(3.1) and H(3.2). If the credible interval in 11) / 12) does not contain 0, then there is evidence that men smokers mean outcome difference between the organic / natural condition relative to the own brand condition and convention condition relative to own brand condition differs from the women smokers mean outcome difference between the organic / natural condition relative to the own brand condition and convention condition relative to own brand condition, which would provide evidence against the null hypothesis in H(3.3) and H(3.4) (assuming the direction of the difference is not opposite the hypothesized direction).

Biomarker analyses

Previous work, including our preliminary biosample analyses, demonstrate that short exposures similar to our 15 min ad lib bout increase exposure biomarkers like saliva nicotine (>200-fold) and aldehydes (2-10-fold).^{54,55} Participants' saliva samples (before and after tobacco use sessions) will be characterized for nicotine and aldehyde concentrations and compared across descriptor conditions.

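### The first fallback for the aldehyde outcome, logging a pre/post difference, is undefined for changes at or below zero, and the session's pre-smoking value is not named as a covariate

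*Combined protocol and SAP*

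**What the plan says.** H1.4, a primary hypothesis, is framed in Aims & Hypotheses as "Change in salivary aldehyde concentrations pre/post administration of the study cigarette(s"). The Statistical analyses section, under the heading for H(1.4), H(2.4) and H(3.4), defines the outcome: "Concentrations of formaldehyde and acetaldehyde will be used as the outcome (difference between pre- and post-visit"). Normal errors are expected. If that fails, "a transformed outcome (e.g. log-transformation) will first be explored". The second step is dichotomisation: "if normality still does not hold, then we will consider a binary outcome using a median cutoff". There is no offset, no rule for zero or negative changes, and no statement that concentrations would be logged before differencing.

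On sampling, the section on biomarkers and saliva collection says: "Saliva samples will be collected from the participants before and after each ad lib tobacco product use bout in Sessions 2-5". Study procedures places the first sample of Sessions 3-5 ahead of the introduction of that day's cigarette.

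On covariates, Statistical analyses names "score on the organic products scale, age, education, heaviness of smoking, perceived health, and own brand total puff volume" and adds that "other covariates collected at baseline (e.g. race, ethnicity) will also be considered in the model". No saliva is scheduled at the baseline visit. Slightly earlier, the same section has a general clause that admits other covariates thought to predict the outcome. It does not mention the pre-smoking concentration.

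Biomarker analyses describes the expected response as multiplicative: "aldehydes (2-10-fold").

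**The concern.** The aldehyde paragraph uses the same fallback as the total puff volume paragraph. Puff volume is positive, so its log exists. A difference can be zero or negative, and the sessions for which the log then fails are those with the least response. An analyst who reaches this step must drop those sessions, add an arbitrary constant or go on to a median split. The split discards information and changes what a primary hypothesis estimates.

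Separately, each smoking session supplies a pre-smoking concentration which, in Sessions 3-5, cannot be affected by the descriptor shown that day. That makes it a sound session-level covariate, and the samples are already scheduled. As the plan stands, the value enters only through subtraction, which fixes its coefficient at 1 whether or not that suits the data.

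**Working it through.** **The plan's own figure.** The documents give no power or SD for aldehydes. The only Aim 1 sample size is for total puff volume. With the effect halved to 60 ml, SD = 165 × √1.5 = 202.1 ml and correlation 0.5, the SD of a within-person difference is 202.1 × √(2 × 0.5) = 202.1 ml. Then n = (202.1 × (1.960 + 1.282) / 60)² = 119.2, which rounds up to the stated 120. The figure reproduces, but it says nothing about aldehydes. What follows rests on assumed ranges.

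**Step 1: how often the log is undefined.** Assume the post/pre ratio is lognormal with median F and log-scale SD s. Then P(change ≤ 0) = Φ(−ln F / s). For example, F = 2 and s = 0.5 gives Φ(−0.693/0.5) = Φ(−1.386) = 8.3%. Counts are out of 228 completers × 3 descriptor sessions = 684 changes per aldehyde.

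| Median rise | s = 0.3 | s = 0.5 | s = 0.75 | s = 1.0 |
|---|---|---|---|---|
| 2-fold | 1.0% (7) | 8.3% (57) | 17.8% (122) | 24.4% (167) |
| 4.5-fold | 0.0% (0) | 0.1% (1) | 2.2% (15) | 6.6% (45) |
| 10-fold | 0.0% (0) | 0.0% (0) | 0.1% (1) | 1.1% (7) |

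At 4.5-fold or more the share is about 0–2% unless s exceeds 0.75. At 2-fold it is roughly 1–24%. The values 2 and 10 are the ends of the plan's range; 4.5 is the geometric middle, √(2 × 10) = 4.47.

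**Step 2: what covariate adjustment gains.** Let k be the ratio of the post-smoking to the pre-smoking within-person SD, and r the within-session pre/post correlation. Adjusting for the pre value multiplies the residual variance of the change score by k²(1 − r²) / (k² + 1 − 2rk).

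| k | r = 0 | r = 0.3 | r = 0.5 | r = 0.7 |
|---|---|---|---|---|
| 1 | 0.50 | 0.65 | 0.75 | 0.85 |
| 2 | 0.80 | 0.96 | 1.00 | 0.93 |
| 5 | 0.96 | 0.99 | 0.89 | 0.67 |
| 10 | 0.99 | 0.96 | 0.82 | 0.59 |

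The gain disappears when rk is near 1, because the best coefficient is then the 1 that subtraction already imposes. If the log SDs before and after smoking are equal, k on the raw scale equals the fold rise and k on the log scale is 1. The halving at k = 1, r = 0 is therefore mainly a log-scale gain over the log ratio. On the raw scale with a multi-fold rise, the gain is small unless r is high.

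**Step 3: the candidate analyses together.** Data were simulated for 228 people with lognormal concentrations, a 2- to 10-fold rise and a 16% condition effect. The log-scale SDs were 0.5 between persons, 0.5 within person after smoking and 0.4 or 0.6 within person before smoking, with r from 0 to 0.6. Power of the paired comparison was:

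- raw difference: 61–88%
- log ratio: 51–97%
- log(post) adjusted for log(pre): 87–98%, best or tied in every scenario

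The log ratio sometimes fell below the raw difference, as Step 2 predicts when r is low. Skewness of the raw change was about 2 to 3 across most of these settings, so the Normality fallback could plausibly be reached.

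**The case against.** The strongest reply is that the plan commits to none of this. Log is an example, and it is only to be explored. The wording could be read as logging each concentration and then differencing, which is defined for any positive values. An analyst who met negative changes would see the problem, and a median split comes next. This stands in part: the text does not oblige anyone to discard sessions. But the reading that rescues the log is not written, and it leads to the log ratio, which can be weaker than the raw difference.

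A reader might infer that the pre-smoking value is not used at all. The documents do not support that: it enters through the difference, and the general covariate clause would admit it. It is only not named.

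A reader might also infer that the fallback would bias the condition contrast. No bias has been calculated, and with a large rise the affected sessions are few.

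The power ranges are open to challenge too. With an assumed residual log SD of 0.4 instead of 0.5, the raw difference alone reached 88–99% power. A mixed model with log(pre), whose slope mixes between-person and within-person association, had 1 to 4 points less power than the paired regression, although its condition estimate stayed unbiased. None of these tests is the planned Bayesian model with covariate averaging. Finally, a change score is legitimate in a within-person design, and moving to ratios alters the estimand. These objections limit the size of the claim. They do not make the log of a non-positive number exist.

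**Conclusion.** The point holds in a limited form. The first stated remedy for non-normality does not work for the outcome as defined, and a useful session-level covariate is left to an open clause. If concentrations are lognormal, the log fails in about 0–2% of sessions at a 4.5-fold or larger rise with log-ratio SD up to 0.75, and in roughly 1–24% at 2-fold over SDs of 0.3 to 1.0. Adjustment lowers residual variance by anything from a negligible amount to about half. Because the documents give no aldehyde SD, pre-smoking level or pre/post correlation, the power figures are illustrations only. They do not show that the trial is underpowered for H1.4.

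**What to change.** 1. Name the session's pre-smoking concentration as a prespecified session-level covariate for the aldehyde outcomes, in every model and not subject to selection or averaging. This keeps the change in concentration as the outcome.
2. Replace logging the difference with log(post) adjusted for that session's log(pre), with condition effects reported as ratios. Place it before any median split. A simple log ratio is not an adequate substitute.
3. State how pre and post values below the assay limits are handled. Biomarker analyses lists LOD and LOQ of 0.34 and 1.13 ng/ml for formaldehyde and 0.41 and 1.37 ng/ml for acetaldehyde. Missing data excludes only samples of insufficient volume.

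No new samples or visits are needed. Item 1 is a small SAP change. Item 2 is more than wording: when the fallback is used, the effect becomes a ratio instead of a difference in ng/ml, and the SAP should say so against H1.4, H2.4 and H3.4. Item 3 takes some care, because low values are plausible after 12 hours of abstinence and a censored covariate is harder to handle than a censored outcome.
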